Finally, for exploratory purposes, we will calculate pre-post effect sizes for subgroups of interest to explore whether interventions are comparably efficacious by focal diagnosis, gender, and racial/ethnic identity. Stratification was used to reduce the variation in potential confounders to be spread similarly between conditions, but that is not always entirely successful, especially in a small pilot trial. Therefore, we will conduct exploratory analyses including measured covariates as potential confounders or effect modifiers in the model-building process.

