Cell Phone Support to Promote Medication Adherence Among Adolescents and Young Adults With Chronic Illness

NCT04241627

8/8/2022

This randomized pilot trial tested three different digital health interventions against one another (CPS-C, n = 11, CPS-T, n = 12, and ATR, n = 11). We are interested in the impact on self-reported medication adherence. We have 6 different measures of dependent variables (VAS1w, VAS2w, VAS3w, VAS1m, VAS2m, VAS3m). We assessed our dependent variables 4 occasions, at 0 weeks (pre-tx), 6 weeks (mid-tx), 12 weeks (post-tx), and 18 weeks (follow-up). We would like to run mixed-effect models to test for intervention effects of 1) both CPS conditions (CPS-C and CPS-T, n = 23) versus ATR (n = 11); and 2) the CPS conditions against each other, ignoring ATR (CPS-C, n = 11 versus CPS-T, n = 12). I also have covariates (sex assigned at birth, diagnosis, age) that we can include during nested model building procedures, and include in final reported models if they lead to best fit.

Can we begin by examining the distributions of our dependent variables, and discuss whether we should use linear mixed-effects models; otherwise, we may need to transform or dichotomize the outcome or use a different type of model (poisson? Negative binomial?) to ensure model assumptions are met?

Then, can we evaluate the impact of missing data on my results by re-running these analyses using inverse probably weighting. It is possible that missing data will not be completely at random (i.e., participants with lower medication adherence may also be less likely to adhere to the online survey schedule).

Finally, I would like to calculate effect sizes for subgroups (see the final table). See tables on the next pages.

Blank Tables

Table 5

Best-Fitting Models Predicting Self-Reported Adherence for Both CPS Conditions (C and T) versus ATR (N = 34)

Dependent Variables	VAS1w			VAS2w			VAS3w			VAS1m			VAS2m			VAS3m		
	Estimates	CI	p															
Fixed Effects																		
Intercept																		
Time																		
Intervention Group (both CPS versus ATR)																		
Random Effects																		
σ^2																		
τ_{00}																		
τ_{11}																		
ρ_{01}																		
ICC																		
N																		
Observations																		
Marginal R ² / Conditional R ²																		
AIC																		

Note—Make ATR the reference group so the estimate tells us how the combined CPS groups compare

Table 6

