Best-Fitting Models Predicting Self-Reported Adherence for CPS-T versus CPS-C (N = 23)

Dependent Variables	VAS1w			VAS2w			VAS3w			VAS1m			VAS2m			VAS3m		
	Estimates	CI	p															
Fixed Effects																		
Intercept																		
Time																		
Intervention Group (CPS-T versus CPS-C)																		
Random Effects																		
σ^2																		
τ_{00}																		
τ_{11}																		
ρ_{01}																		
ICC																		
N																		
Observations																		
Marginal R ² / Conditional R ²																		
AIC																		

Note—Make CPS-C the reference group so the estimate tells us how CPS-T compares

Table 7

Exploratory Analyses Estimating Effect Sizes Using Self-Reported Outcomes Past Week (Pre-Post... Baseline to 12 weeks)

Subgroup	n	d	CI	p	Subgroup	n	d	CI	p
VAS1w									
Total Sample	--	--	--	--	Young Men	--	--	--	--
CPS Combined vs. ATR	34				CPS Combined vs. ATR				
CPS-T vs. CPS-C					CPS-T vs. CPS-C				
Sickle Cell Disease	--	--	--	--	Young Women	--	--	--	--
CPS Combined vs. ATR	14				CPS Combined vs. ATR				
CPS-T vs. CPS-C					CPS-T vs. CPS-C				
Solid Organ Transplant	--	--	--	--	Latinx	--	--	--	--
CPS Combined vs. ATR	10				CPS Combined vs. ATR				
CPS-T vs. CPS-C					CPS-T vs. CPS-C				
Type 2 Diabetes	--	--	--	--	Black	--	--	--	--
CPS Combined vs. ATR	10				CPS Combined vs. ATR				
CPS-T vs. CPS-C					CPS-T vs. CPS-C				
VAS2w									
Total Sample (N = 34)	--	--	--	--	Young Men	--	--	--	--
CPS Combined vs. ATR					CPS Combined vs. ATR				
CPS-T vs. CPS-C					CPS-T vs. CPS-C				
Sickle Cell Disease (n = 14)	--	--	--	--	Young Women	--	--	--	--
CPS Combined vs. ATR					CPS Combined vs. ATR				
CPS-T vs. CPS-C					CPS-T vs. CPS-C				
Solid Organ Transplant (n = 10)	--	--	--	--	Latinx	--	--	--	--
CPS Combined vs. ATR					CPS Combined vs. ATR				
CPS-T vs. CPS-C					CPS-T vs. CPS-C				
Type 2 Diabetes (n = 10)	--	--	--	--	Black	--	--	--	--
CPS Combined vs. ATR					CPS Combined vs. ATR				
CPS-T vs. CPS-C					CPS-T vs. CPS-C				
VAS3w									
Total Sample (N = 34)	--	--	--	--	Young Men	--	--	--	--
CPS Combined vs. ATR					CPS Combined vs. ATR				
CPS-T vs. CPS-C					CPS-T vs. CPS-C				
Sickle Cell Disease (n = 14)	--	--	--	--	Young Women	--	--	--	--
CPS Combined vs. ATR					CPS Combined vs. ATR				
CPS-T vs. CPS-C					CPS-T vs. CPS-C				

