Solid Organ Transplant (n = 10)	--	--	--	--	Latinx	--	--	--	--
CPS Combined vs. ATR					CPS Combined vs. ATR				
CPS-T vs. CPS-C					CPS-T vs. CPS-C				
Type 2 Diabetes (n = 10)	--	--	--	--	Black	--	--	--	--
CPS Combined vs. ATR					CPS Combined vs. ATR				
CPS-T vs. CPS-C					CPS-T vs. CPS-C				

Table 8

Exploratory Analyses Estimating Effect Sizes Using Self-Reported Outcomes Past Month

Subgroup	n	d	CI	p	Subgroup	n	d	CI	p
VAS1m									
Total Sample	--	--	--	--	Young Men	--	--	--	--
CPS Combined vs. ATR					CPS Combined vs. ATR				
CPS-T vs. CPS-C					CPS-T vs. CPS-C				
Sickle Cell Disease	--	--	--	--	Young Women	--	--	--	--
CPS Combined vs. ATR					CPS Combined vs. ATR				
CPS-T vs. CPS-C					CPS-T vs. CPS-C				
Solid Organ Transplant	--	--	--	--	Latinx	--	--	--	--
CPS Combined vs. ATR					CPS Combined vs. ATR				
CPS-T vs. CPS-C					CPS-T vs. CPS-C				
Type 2 Diabetes	--	--	--	--	Black	--	--	--	--
CPS Combined vs. ATR					CPS Combined vs. ATR				
CPS-T vs. CPS-C					CPS-T vs. CPS-C				
VAS2m									
Total Sample	--	--	--	--	Young Men	--	--	--	--
CPS Combined vs. ATR					CPS Combined vs. ATR				
CPS-T vs. CPS-C					CPS-T vs. CPS-C				
Sickle Cell Disease	--	--	--	--	Young Women	--	--	--	--
CPS Combined vs. ATR					CPS Combined vs. ATR				
CPS-T vs. CPS-C					CPS-T vs. CPS-C				
Solid Organ Transplant	--	--	--	--	Latinx	--	--	--	--
CPS Combined vs. ATR					CPS Combined vs. ATR				
CPS-T vs. CPS-C					CPS-T vs. CPS-C				
Type 2 Diabetes	--	--	--	--	Black	--	--	--	--
CPS Combined vs. ATR					CPS Combined vs. ATR				
CPS-T vs. CPS-C					CPS-T vs. CPS-C				
VAS3m									
Total Sample (N = 34)	--	--	--	--	Young Men	--	--	--	--
CPS Combined vs. ATR					CPS Combined vs. ATR				
CPS-T vs. CPS-C					CPS-T vs. CPS-C				
Sickle Cell Disease (n = 14)	--	--	--	--	Young Women	--	--	--	--
CPS Combined vs. ATR					CPS Combined vs. ATR				
CPS-T vs. CPS-C					CPS-T vs. CPS-C				
Solid Organ Transplant (n = 10)	--	--	--	--	Latinx	--	--	--	--
CPS Combined vs. ATR					CPS Combined vs. ATR				
CPS-T vs. CPS-C					CPS-T vs. CPS-C				
Type 2 Diabetes (n = 10)	--	--	--	--	Black	--	--	--	--
CPS Combined vs. ATR					CPS Combined vs. ATR				
CPS-T vs. CPS-C					CPS-T vs. CPS-C

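### Whether CPS works equally well across subgroups is a between-subgroup question, but the SAP reports only 84 separate within-subgroup effect sizes and p-values and specifies no interaction estimate

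*Protocol*

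**What the plan says.** The closing paragraph of the Protocol's Analytic Plan states the aim and the method together. Effect sizes for pre-post change are to be worked out within subgroups, as an exploratory step, and the stated purpose is to "explore whether interventions are comparably efficacious by focal diagnosis, gender, and racial/ethnic identity". The paragraph then adds a second route: "we will conduct exploratory analyses including measured covariates as potential confounders or effect modifiers in the model-building process". No interaction term, outcome or contrast is named for that route.

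The SAP asks only for subgroup effect sizes: "Finally, I would like to calculate effect sizes for subgroups (see the final table". It lists sex, diagnosis and age as covariates for model building, leaves out race/ethnicity, and mentions no interaction. The fixed-effect rows in the shells for Tables 5 and 6 are intercept, time and intervention group.

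Table 7 ("Exploratory Analyses Estimating Effect Sizes Using Self-Reported Outcomes Past Week", baseline to 12 weeks) and Table 8 ("Exploratory Analyses Estimating Effect Sizes Using Self-Reported Outcomes Past Month") have columns for n, d, CI and p. Besides a total-sample block, each has seven subgroups: three diagnoses, young men, young women, Latinx and Black. Each subgroup has two contrast rows, "CPS Combined vs. ATR" and CPS-T against CPS-C. On outcomes the SAP says: "We have 6 different measures of dependent variables (VAS1w, VAS2w, VAS3w, VAS1m, VAS2m, VAS3m". Neither document mentions multiplicity.

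**The concern.** Whether an intervention is comparably efficacious in two groups depends on the difference between the two effects and its uncertainty. A d and p inside each group do not supply that. A p below 0.05 in one diagnosis and above it in another is compatible with identical effects, particularly when the groups hold 14, 10 and 10 people spread over three arms.

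The risk is that Tables 7 and 8 are read by scanning the p columns. CPS would then seem to work in some diagnoses or ethnic groups and not in others when the data cannot distinguish them. The Protocol's Research Aims describe the pilot as preparation for a fully powered multisite trial, so such a pattern could carry into later thinking.

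**Working it through.** **Inputs from the documents.** N = 34, with CPS-C 11, CPS-T 12 and ATR 11 (SAP). Diagnosis groups of 14, 10 and 10 (Table 7). Planning effect d = 0.85, about 87% power, planned 40 v 20 (Protocol, Power Analysis and Analytic Plan).

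**Assumptions.** The documents state neither alpha nor sidedness, so two-sided 0.05 is assumed. Also assumed are CPS v ATR splits of 9/5 in sickle cell disease and 7/3 in each of the other two diagnoses (these add to 23 v 11), the sex and ethnicity counts, and the correlation between VAS items.

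**The plan's own figure.** A two-sample comparison of 40 v 20 at d = 0.85, two-sided 0.05, has power 0.874 (normal) or 0.863 (noncentral t), in line with the stated 87%. At the SAP's 23 v 11 the noncentral t gives 0.61 for the total sample, before any subgrouping.

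**Count.** 7 subgroups x 2 contrasts x 6 scores = 84 cells. The total-sample rows add 2 x 6 = 12, making 96.

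**Chance findings under a global null.**
- Expected number below 0.05: 84 x 0.05 = 4.2, whatever the correlation between tests.
- At least one, if all tests were independent: 1 - 0.95^84 = 0.987.
- At least one, simulated with overlapping subgroups (1,500 trials per setting): about 97%, 94%, 85% and 68% at between-item correlations of 0, 0.5, 0.8 and 0.95.

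**Identical true effect, d = 0.85, in every diagnosis.** The noncentrality is d / sqrt(1/n1 + 1/n2) with n1 + n2 - 2 degrees of freedom.
- Power: 0.289 (9 v 5), 0.193 and 0.193 (7 v 3 twice).
- All three significant: 0.289 x 0.193 x 0.193 = 0.011.
- None significant: 0.711 x 0.807 x 0.807 = 0.463.
- Diagnoses disagree on significance: 1 - 0.011 - 0.463 = 0.526, about 53%. With 6/4 splits in the two groups of 10 it is about 55%.
- Simulated median gap between the largest and smallest observed diagnosis d: 1.17 when the true d is 0.85 throughout, and 1.11 when it is zero.

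**Precision of single cells.** The approximate 95% half-width is t x sqrt(1/n1 + 1/n2), in SD units: 1.2 for 9 v 5, 1.6 for 7 v 3, and 2.0 for an assumed 4 v 3 CPS-T v CPS-C cell. Using 1.96 in place of t gives 1.1, 1.35 and 1.5.

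**What an interaction estimate would give.**
- Sickle cell disease v type 2 diabetes: SE of the difference in d = sqrt(1/9 + 1/5 + 1/7 + 1/3) = 0.89. Power for a difference of 0.85 is Phi(0.85/0.89 - 1.96), about 16%. The difference detectable with 80% power is 2.80 x 0.89, about 2.5 SD.
- Gender, assuming an even split: SE = sqrt(2 x (1/11.5 + 1/5.5)) = 0.73. Power is about 21%, and the detectable difference is about 2.05 SD.

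**The case against.** Four points can fairly be made for the plan.

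1. **The Protocol does foresee effect modification.** A reader of Tables 7 and 8 alone might infer that the plan has no provision for interactions. The effect-modifier sentence rules that reading out, since examining a covariate as an effect modifier in a regression means some form of arm-by-covariate term. What remains is that the analysis is unspecified in the Protocol and absent from the SAP and its shells, so nothing commits anyone to produce it.
2. **The analyses are labelled exploratory**, in the Protocol and in both table titles. The Power Analysis concedes reduced subgroup power, and d and CI stand beside p. This limits the claim being made and lowers the potential harm. It does not turn within-group p-values into a comparison between groups.
3. **False differences are not certain.** The 84 tests are correlated, and the chance of at least one p below 0.05 depends on assumptions. A small p misleads about comparability only if readers set significance in one row against another, and no passage tells them to. This stands: the claim is about what is likely.
4. **The better method will not settle the question either.** At about 16% to 21% power for a difference of 0.85, an interaction interval will be wide. That also stands. The gain is that the interval shows the uncertainty on the question asked, which the present tables leave out.

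**Conclusion.** The point holds in a limited form. The plan's question is about differences between subgroups. The output the SAP specifies has 84 within-subgroup results and no between-subgroup contrast, and the effect modification mentioned in the Protocol is not carried forward. That conclusion rests on the text and table shells alone and needs no assumption.

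The size of the risk does rest on assumptions: two-sided 0.05, the arm splits, the sex and ethnicity counts and the item correlation. Under them, about 4.2 nominally significant cells are expected under a global null, and the chance of at least one is 68% to 97%. With identical true effects of d = 0.85, the diagnoses disagree on significance about 53% of the time, and a gap of 1.1 to 1.2 in observed d is typical.

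Two stronger readings are not supported. A reader might infer that the trial is bound to report spurious subgroup differences; the figures make that likely, not certain. A reader might also infer that subgroup results will choose the populations for the multisite trial. The Protocol says only that the pilot prepares for that trial, and its background argues for a general intervention across diagnoses.

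**What to change.** In the SAP, for each of the three factors:

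- Name one VAS score and fit one full-sample model, with CPS combined v ATR as the arm contrast.
- Target the baseline-to-12-week effect: either the 12-week value adjusted for baseline with arm x factor, or arm x time x factor in the mixed model. A plain arm x factor term in a repeated-measures model shaped like Tables 5 and 6 would average over week 0, before any intervention.
- Define the factors: diagnosis; gender, using the young men/young women grouping already in Tables 7 and 8; and race/ethnicity, with its coding stated, since the shells have only Latinx and Black rows.
- Report the interaction estimate with its 95% CI as the exploratory answer on comparability.

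In Tables 7 and 8, keep subgroup d and CI as descriptive, delete p for the subgroup rows, and show CPS-T v CPS-C within diagnosis descriptively only.

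The cost is SAP wording and revised shells, with no new data. The downside is plain imprecision: an SE of about 0.7 to 0.9 SD under the assumed splits. The report should therefore say that 34 participants cannot establish comparability, and that an interval covering zero is not evidence of equal effects.

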### **Missing Data Plan**

I will evaluate the impact of missing data on my results by re-running these analyses using inverse probability weighting. It is possible that missing data will not be completely at random (i.e., participants with lower medication adherence may also be less likely to adhere to the online survey schedule).

### **Power Analysis**

Using STATA SE Version 15 software, we estimated the statistical power achieved with our proposed sample, assuming the Cohen's  $d$  effect size of 0.85 between groups seen in our preliminary data, within-subject intra-class correlation of 0.5 for repeated measures. We used the

design effect for clustered data (3 post-baseline measures, intraclass correlation=0.5) to compute the effective sample size for each group. The table below shows estimated power to detect differences in CPS (combined) versus automated reminders, and for the comparison of CPS strategies (original vs live text) in the total sample and by medical condition. To be more conservative, we also provide the statistical power for the CPS comparisons with a smaller effect size of 0.75 and 0.50. We also computed power to detect simple pre/post (e.g., baseline-12 week) changes between groups. There is approximately 87% statistical power for group comparisons using the combined sample with the effect size of 0.85; power is reduced for subgroup comparisons and the smaller effect size. However, as this study is a pilot randomized trial, the sample is more than sufficient to estimate effect sizes and assess feasibility for use in future proposals. See Table 1 for details.

Cell Phone Support to Promote Medication Adherence Among Adolescents and Young Adults With Chronic Illness

NCT04241627

8/8/2022

This randomized pilot trial tested three different digital health interventions against one another (CPS-C, n = 11, CPS-T, n = 12, and ATR, n = 11). We are interested in the impact on self-reported medication adherence. We have 6 different measures of dependent variables (VAS1w, VAS2w, VAS3w, VAS1m, VAS2m, VAS3m). We assessed our dependent variables 4 occasions, at 0 weeks (pre-tx), 6 weeks (mid-tx), 12 weeks (post-tx), and 18 weeks (follow-up). We would like to run mixed-effect models to test for intervention effects of 1) both CPS conditions (CPS-C and CPS-T, n = 23) versus ATR (n = 11); and 2) the CPS conditions against each other, ignoring ATR (CPS-C, n = 11 versus CPS-T, n = 12). I also have covariates (sex assigned at birth, diagnosis, age) that we can include during nested model building procedures, and include in final reported models if they lead to best fit.

Can we begin by examining the distributions of our dependent variables, and discuss whether we should use linear mixed-effects models; otherwise, we may need to transform or dichotomize the outcome or use a different type of model (poisson? Negative binomial?) to ensure model assumptions are met?

Then, can we evaluate the impact of missing data on my results by re-running these analyses using inverse probably weighting. It is possible that missing data will not be completely at random (i.e., participants with lower medication adherence may also be less likely to adhere to the online survey schedule).

Finally, I would like to calculate effect sizes for subgroups (see the final table). See tables on the next pages.

Blank Tables

Table 5

Best-Fitting Models Predicting Self-Reported Adherence for Both CPS Conditions (C and T) versus ATR (N = 34)

Dependent Variables	VAS1w			VAS2w			VAS3w			VAS1m			VAS2m			VAS3m		
	Estimates	CI	p															
Fixed Effects																		
Intercept																		
Time																		
Intervention Group (both CPS versus ATR)																		
Random Effects																		
σ^2																		
τ_{00}																		
τ_{11}																		
ρ_{01}																		
ICC																		
N																		
Observations																		
Marginal R ² / Conditional R ²																		
AIC																		

Note—Make ATR the reference group so the estimate tells us how the combined CPS groups compare

Table 6

Best-Fitting Models Predicting Self-Reported Adherence for CPS-T versus CPS-C (N = 23)

Dependent Variables	VAS1w			VAS2w			VAS3w			VAS1m			VAS2m			VAS3m		
	Estimates	CI	p															
Fixed Effects																		
Intercept																		
Time																		
Intervention Group (CPS-T versus CPS-C)																		
Random Effects																		
σ^2																		
τ_{00}																		
τ_{11}																		
ρ_{01}																		
ICC																		
N																		
Observations																		
Marginal R ² / Conditional R ²																		
AIC																		

Note—Make CPS-C the reference group so the estimate tells us how CPS-T compares

Table 7

Exploratory Analyses Estimating Effect Sizes Using Self-Reported Outcomes Past Week (Pre-Post... Baseline to 12 weeks)

Subgroup	n	d	CI	p	Subgroup	n	d	CI	p
VAS1w									
Total Sample	--	--	--	--	Young Men	--	--	--	--
CPS Combined vs. ATR	34				CPS Combined vs. ATR				
CPS-T vs. CPS-C					CPS-T vs. CPS-C				
Sickle Cell Disease	--	--	--	--	Young Women	--	--	--	--
CPS Combined vs. ATR	14				CPS Combined vs. ATR				
CPS-T vs. CPS-C					CPS-T vs. CPS-C				
Solid Organ Transplant	--	--	--	--	Latinx	--	--	--	--
CPS Combined vs. ATR	10				CPS Combined vs. ATR				
CPS-T vs. CPS-C					CPS-T vs. CPS-C				
Type 2 Diabetes	--	--	--	--	Black	--	--	--	--
CPS Combined vs. ATR	10				CPS Combined vs. ATR				
CPS-T vs. CPS-C					CPS-T vs. CPS-C				
VAS2w									
Total Sample (N = 34)	--	--	--	--	Young Men	--	--	--	--
CPS Combined vs. ATR					CPS Combined vs. ATR				
CPS-T vs. CPS-C					CPS-T vs. CPS-C				
Sickle Cell Disease (n = 14)	--	--	--	--	Young Women	--	--	--	--
CPS Combined vs. ATR					CPS Combined vs. ATR				
CPS-T vs. CPS-C					CPS-T vs. CPS-C				
Solid Organ Transplant (n = 10)	--	--	--	--	Latinx	--	--	--	--
CPS Combined vs. ATR					CPS Combined vs. ATR				
CPS-T vs. CPS-C					CPS-T vs. CPS-C				
Type 2 Diabetes (n = 10)	--	--	--	--	Black	--	--	--	--
CPS Combined vs. ATR					CPS Combined vs. ATR				
CPS-T vs. CPS-C					CPS-T vs. CPS-C				
VAS3w									
Total Sample (N = 34)	--	--	--	--	Young Men	--	--	--	--
CPS Combined vs. ATR					CPS Combined vs. ATR				
CPS-T vs. CPS-C					CPS-T vs. CPS-C				
Sickle Cell Disease (n = 14)	--	--	--	--	Young Women	--	--	--	--
CPS Combined vs. ATR					CPS Combined vs. ATR				
CPS-T vs. CPS-C					CPS-T vs. CPS-C				
Solid Organ Transplant (n = 10)	--	--	--	--	Latinx	--	--	--	--
CPS Combined vs. ATR					CPS Combined vs. ATR				
CPS-T vs. CPS-C					CPS-T vs. CPS-C				
Type 2 Diabetes (n = 10)	--	--	--	--	Black	--	--	--	--
CPS Combined vs. ATR					CPS Combined vs. ATR				
CPS-T vs. CPS-C					CPS-T vs. CPS-C				

Table 8

Exploratory Analyses Estimating Effect Sizes Using Self-Reported Outcomes Past Month

Subgroup	n	d	CI	p	Subgroup	n	d	CI	p
VAS1m									
Total Sample	--	--	--	--	Young Men	--	--	--	--
CPS Combined vs. ATR					CPS Combined vs. ATR				
CPS-T vs. CPS-C					CPS-T vs. CPS-C				
Sickle Cell Disease	--	--	--	--	Young Women	--	--	--	--
CPS Combined vs. ATR					CPS Combined vs. ATR				
CPS-T vs. CPS-C					CPS-T vs. CPS-C				
Solid Organ Transplant	--	--	--	--	Latinx	--	--	--	--
CPS Combined vs. ATR					CPS Combined vs. ATR				
CPS-T vs. CPS-C					CPS-T vs. CPS-C				
Type 2 Diabetes	--	--	--	--	Black	--	--	--	--
CPS Combined vs. ATR					CPS Combined vs. ATR				
CPS-T vs. CPS-C					CPS-T vs. CPS-C				
VAS2m									
Total Sample	--	--	--	--	Young Men	--	--	--	--
CPS Combined vs. ATR					CPS Combined vs. ATR				
CPS-T vs. CPS-C					CPS-T vs. CPS-C				
Sickle Cell Disease	--	--	--	--	Young Women	--	--	--	--
CPS Combined vs. ATR					CPS Combined vs. ATR				
CPS-T vs. CPS-C					CPS-T vs. CPS-C				
Solid Organ Transplant	--	--	--	--	Latinx	--	--	--	--
CPS Combined vs. ATR					CPS Combined vs. ATR				
CPS-T vs. CPS-C					CPS-T vs. CPS-C				
Type 2 Diabetes	--	--	--	--	Black	--	--	--	--
CPS Combined vs. ATR					CPS Combined vs. ATR				
CPS-T vs. CPS-C					CPS-T vs. CPS-C				
VAS3m									
Total Sample (N = 34)	--	--	--	--	Young Men	--	--	--	--
CPS Combined vs. ATR					CPS Combined vs. ATR				
CPS-T vs. CPS-C					CPS-T vs. CPS-C				
Sickle Cell Disease (n = 14)	--	--	--	--	Young Women	--	--	--	--
CPS Combined vs. ATR					CPS Combined vs. ATR				
CPS-T vs. CPS-C					CPS-T vs. CPS-C				
Solid Organ Transplant (n = 10)	--	--	--	--	Latinx	--	--	--	--
CPS Combined vs. ATR					CPS Combined vs. ATR				
CPS-T vs. CPS-C					CPS-T vs. CPS-C				
Type 2 Diabetes (n = 10)	--	--	--	--	Black	--	--	--	--
CPS Combined vs. ATR					CPS Combined vs. ATR				
CPS-T vs. CPS-C					CPS-T vs. CPS-C
